A total of 280 participants who are patients at UAB and UNC - enrolled in CNICS, experiencing chronic pain (Brief Chronic Pain Screening Questionnaire (BCPQ) = at least moderate pain for at least 3 months) and moderately severe and impairing chronic pain (PEG pain questionnaire = average of all three times is 4 or greater).

Inclusion Criteria

1. Enrolled in CNICS
2. Age \geq 18 years
3. English-speaking
4. Chronic pain (Brief Chronic Pain Screening Questionnaire (BCPQ) = at least moderate pain for at least 3 months)

5. Moderately severe and impairing chronic pain (PEG pain questionnaire = average of all three items is 4 or greater)
6. Ability and willingness to attend the group sessions at the date/time specified
7. No plans for major surgery during the study period that would interfere with study procedures.

Exclusion Criteria

1. Do not speak or understand English
2. Are planning a new pain treatment like surgery
3. Cannot attend the group sessions
4. Had previously participated in the pilot study (STOMP)
5. Unwilling to provide informed consent

We will rely heavily on active recruitment using patients identified as having chronic pain on the BCPQ and PEG on CNICS pain Patient Reported Outcome measures.

Additionally, participants will be recruited via word-of-mouth by clinic staff or providers, calls generated from flyer tear-offs and other advertisements placed in the clinic.

b) PRE-SCREENING (phone and then in-person)

Potential participants will be prescreened over the phone using our prescreening phone script once the participating site. A HIPAA waiver will be submitted with the initial submission. If the individual passes the telephone prescreen, he or she will be scheduled for an in-person pre-screening visit by a member of the STOMP recruitment team. The date and time of the pre-screening visit along with the participant contact information and

preferred method of contact will be recorded on the Prescreening Visit Appointment Form. Data from the pre-screening phone call and visit appointment forms will be transferred to a prescreening excel log for accurate tracking. About 48 hours prior to the in-person prescreen visit, a reminder call from the research staff will be made to remind the potential participant of the prescreening visit. If the research staff cannot locate the potential participant after three attempts, the staff will note an inactive status in the prescreening log.

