On the day of the prescreen, the research staff member conducting the prescreen will log onto Redcap and establish a unique RedCap instance for this participant and complete the prescreen section only. Participants will be required to sign a prescreen consent form before the initiation of the session. At the end of the prescreen, the research staff member will record the participant's eligibility on the Prescreening Visit Appointment Form. If the participant is eligible for enrollment, a Screening and Enrollment Visit will be scheduled and recorded on a Screening and Enrollment Visit form. A separate excel log will collect data from the screening and enrollment visit form for tracking purposes. The participant will also be thanked and given their \$25 incentive. If the participant is not eligible, he or she will also be thanked for their time and given a \$25 incentive.

c) SCREENING AND ENROLLMENT

The Screening and Enrollment Visit will be scheduled approximately 2-4 weeks from the date of the pre-screen visit and recorded on a Screening and Enrollment Visit form. Participants will receive a reminder call at about a week and 48 hours prior to the

scheduled screening and enrollment visit. At the beginning of the screening and enrollment visit, the participant will complete the informed consent process, and then they will complete a baseline assessment.

Informed Consent Procedures

Informed consent will be administered by staff trained in accordance to the University of Pittsburgh, the University of Alabama at Birmingham and the University of North Carolina at Chapel Hill's Institutional Review Boards' guidelines for obtaining informed consent. The staff member obtaining consent must verify the following: protocol name, version number, dates for use, and institution. The Study team member will also ensure that the most recent informed consent is being used for the study. Initial informed consent must be completed and documented before any other study related procedures are done.

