Comprehension will be assessed by asking the participant to summarize the study activities or some general open ended questions will be asked like what can you tell me about this study, can you tell me about how long the study may last, etc. The consent process is estimated to take around 30 minutes. Study staff will ensure that the participant has signed and dated the consent form including the HIPAA form. All signed consent forms will be stored in locked file cabinets under respective participant files.

Baseline Assessment

The research staff will then administer the baseline assessment which includes a confirmatory set of screening questions via RedCap. Confirmation of the participant's eligibility will be recorded in RedCap. If a participant is ineligible based on this RedCap assessment, they will be given a \$50 incentive and thanked for their time, and they will

not be considered to have been enrolled in the study at any point (informed consent is asked before this point so that we can use any data generated in published findings). If a participant is eligible, they will also be thanked for coming and given their \$50 incentive payment for their time. Completion of Baseline assessment will be recorded in excel logs.

RANDOMIZATION

Our team will utilize a 1:1 ratio for allocation to the STOMP intervention and Usual Care (UC) conditions. Our study statistician, [name], will use SAS to generate the randomization scheme stratified by whether the participant is on long-term opioid therapy (taking prescribed opioids for at least 3 months) and whether they have chronic multisite pain (pain in at least 3 locations or pain all over). Importantly, the PIs and outcomes assessors will be blinded to intervention vs. comparison allocation. Participants in the intervention and comparison conditions will have full access to all available clinical services at their respective sites.

d) INTERVENTION

The intervention group will receive “treatment as usual” plus the STOMP behavioral intervention. The “treatment as usual” refers to the standard of care that patients receive at the UAB and UNC clinics. This standard of care is for patients to discuss chronic pain with their providers at their discretion. Although highly variable, providers can recommend and prescribe pharmacologic (e.g., opioid and other pain medication), non-pharmacologic (e.g., physical therapy, referral to psychology) approaches for pain. This study will not interfere in any way with usual care.

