There were no covariates included in our models, only time and treatment group indicator. We used linear mixed effects models which do not require adjustment for baseline as a fixed effect as it is included as an outcome. This allows for estimation of treatment effects at all follow-up times that takes into account any baseline differences between groups.

Handling of Missing Values. As a preventive measure, we will make every attempt to document all reasons for missing data. In addition, baseline characteristics will be compared between participants who do and do not withdraw from the study as a way to assess the impact of missing information and attrition. We will also compare the rates of lost-to-follow-up (LTF) between study arms.

Our general assumption will be that missing data is of the Missing at Random (MAR) mechanism. In this case, the use of linear mixed models for the primary analysis will be sufficient in reducing the impact that missing data has on biasing the primary results. Additionally, we will conduct a sensitivity analysis using multiple imputation via chained equations (MICE) to see how robust the overall inferences are.

Statistical Analyses.

The primary outcome – BPI-Total score – and the other secondary outcomes will be assessed as continuous variables. Linear mixed effects models will be performed to test differences between intervention and control conditions at the immediate post intervention and at 3 months. Models will include random effects for participant and therapy group. Therapy group is an identifier of the group of 20 that were randomized to create a STOMP group of 10. Fixed effects will be STOMP indicator, time and STOMP by time interaction. The primary hypothesis will be tested using the least squared means of each group at each time. We will check distributional

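### The primary model takes no precision from pre-randomisation pain scores; a pre-screen PEG, if stored as the protocol implies, should be pre-specified as a covariate alongside baseline BPI-Total

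*Combined protocol and SAP*

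**What the plan says.** **Pre-screen and baseline (protocol, section III).** The inclusion criteria in III.a require "Moderately severe and impairing chronic pain (PEG pain questionnaire = average of all three items is 4 or greater". Under III.b, those who pass a telephone screen attend an in-person pre-screen, where staff "establish a unique RedCap instance for this participant and complete the prescreen section only". Then: "At the end of the prescreen, the research staff member will record the participant's eligibility on the Prescreening Visit Appointment Form". Only those found eligible are booked for enrolment. Under III.c, "The Screening and Enrollment Visit will be scheduled approximately 2-4 weeks from the date of the pre-screen visit", and at that visit staff administer a "baseline assessment which includes a confirmatory set of screening questions via RedCap". The Assessment Table (III.l) gives the pre-baseline contact its own form, Section I, but does not list its items.

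**Model (SAP).** Under Endpoint and Covariates: "There were no covariates included in our models, only time and treatment group indicator". The reason given is that linear mixed models "do not require adjustment for baseline as a fixed effect as it is included as an outcome". Under Statistical Analyses, the fixed effects are the STOMP indicator, time and their interaction, with random effects for participant and therapy group. The primary test uses the least-squares means of each arm at each time. The imputation model draws on earlier outcome data from baseline. Nothing from the pre-screen enters any analysis.

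**The concern.** A pain score taken before randomisation predicts later pain and cannot be affected by treatment. Using it narrows the confidence interval for the treatment effect at almost no cost. The plan appears to collect two such scores on separate days, a PEG at pre-screen and the BPI at baseline, yet the primary contrast as specified uses neither to reduce variance. The SAP treats carrying baseline BPI-Total as an outcome row as a substitute for adjustment. With separate baseline means for each arm, it is not one as far as precision is concerned. What is at stake is the width of the interval for BPI-Total and for the pain secondary outcomes (PEG, BPI severity and BPI interference).

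**Working it through.** **1. The plan's own figure.** Inputs from the SAP's Sample Size Calculation: difference 1, SD 2.4, 210 evaluable (105 per arm at 1:1), two-sample t-test. Alpha is not stated, so 0.05 two-sided is assumed. SE = 2.4 × √(2/105) = 0.331. Noncentral t gives power 85.2% at 105 per arm and 84.9% at 104, so 210 reproduces. 210/(1 − 0.25) = 280 also reproduces. Therapy-group clustering is ignored here and below, as in the SAP's own calculation.

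**2. What the specified contrast uses.** With STOMP, time and STOMP by time all free, each arm has its own mean at each time. With complete data, the fitted means are the observed means. In one simulated complete data set (210 participants, correlation 0.5, participant random effect), the model's post-intervention least-squares mean difference was −1.322 and the raw difference in post means was −1.322. Baseline BPI-Total therefore adds no precision to this contrast.

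**3. Is a pre-screen PEG stored?** The PEG cut-off is an eligibility criterion, eligibility is decided at the end of the in-person pre-screen, a REDCap section is completed there, and the baseline questions are called confirmatory. A PEG asked at the pre-screen is the natural reading. No sentence says that it is asked or that the score is kept.

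**4. Pre-screen PEG alone against the SAP as written.** With a share R² of follow-up variance explained, SE = 0.331 × √(1 − R²). Simulations truncated at PEG ≥ 4 on both visits, with assumed instrument reliability 0.8-0.9 and underlying pain correlated at a constant 0.5-0.8 or decaying over weeks, gave R² of about 0.06-0.35.
- R² = 0.06: SE 0.321, power 87.3%.
- R² = 0.35: SE 0.267, power 96.1%.

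**5. Baseline BPI-Total used efficiently.** The variance factor is 1 − r², where r is the baseline-post correlation.
- r = 0.3: SE 0.316, power 88.3%.
- r = 0.5: SE 0.287, power 93.4%.
- r = 0.7: SE 0.237, power 98.8%.

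**6. PEG on top of baseline BPI-Total.** Write r_b for baseline-post, r_p for PEG-post and r_bp for PEG-baseline. The variance factor with both is 1 − (r_b² + r_p² − 2·r_b·r_p·r_bp)/(1 − r_bp²).

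| r_b, r_p, r_bp | Baseline only | Both | Remaining variance removed | SE reduction | Power |
|---|---|---|---|---|---|
| 0.5, 0.35, 0.7 | 0.750 | 0.750 | 0% | 0% | 93.4% → 93.4% |
| 0.5, 0.4, 0.6 | 0.750 | 0.734 | 2.1% | 1.0% | 93.4% → 93.9% |
| 0.3, 0.3, 0.3 | 0.910 | 0.862 | 5.3% | 2.7% | 88.3% → 89.9% |
| 0.5, 0.5, 0.5 | 0.750 | 0.667 | 11.1% | 5.7% | 93.4% → 95.7% |
| 0.7, 0.7, 0.7 | 0.510 | 0.424 | 17.0% | 8.9% | 98.8% → 99.6% |

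First row: 0.25 + 0.1225 − 0.245 = 0.1275; 0.1275/0.51 = 0.25; 1 − 0.25 = 0.75, the same as without PEG. The equal-correlation rows are an upper bound, because they treat the PEG as being as informative as baseline BPI-Total itself.

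The truncated simulations gave about 2-5% of remaining variance under decaying correlation and 5.5-14.2% under constant correlation. The most favourable of these, 14.2%, is an SE reduction of 1 − √0.858 = 7.4%. At r_b = 0.5 it raises power from 93.4% to 96.3%.

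**The case against.** **The score may not exist in usable form.** The REDCap sentence does not mention pain, the contents of Section I are not shown, and the appointment form could hold a bare yes or no. III.a says recruitment leans on PEG scores already in CNICS, so for some people the screening value might come from there. This stands: a reader might infer that two stored pain scores exist for every randomised participant, and the documents support that only as a strong inference. It is why the fix begins with a check.

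**The power gain is mostly available without the PEG.** This also stands. A reader might take 87-96% as the gain over a properly adjusted analysis. It is the figure for PEG alone against no adjustment. Beyond baseline BPI-Total the PEG is an older score, from a different instrument, truncated at 4, and its increment can be nil.

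**The model does use baseline.** The SAP says its approach takes account of baseline differences. If the test were read as a difference in change from baseline, the variance factor would be 2(1 − r). That equals the unadjusted variance at r = 0.5, is worse below it (power 71.9% at r = 0.3) and better above it (97.3% at r = 0.7). It exceeds 1 − r² by the ratio 2/(1 + r), so efficient adjustment still does better. With missing follow-up, the baseline row also helps the model handle dropout. The exact equality in step 2 is for complete data.

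**An unadjusted randomised comparison is valid.** Agreed. A reader might infer bias, inflated type I error or an underpowered trial. None follows: the 210 was derived for an unadjusted t-test and does not rely on any covariate gain.

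**Conclusion.** The point holds as a lost-precision finding. As specified, the primary contrast gains nothing from pre-randomisation pain scores when data are complete. The larger part of the recoverable precision usually lies in baseline BPI-Total, and a pre-screen PEG is a smaller addition that depends on its being stored. Relative to 85.2% power as planned, PEG alone gives about 87-96%. Once baseline BPI-Total is used efficiently, PEG removes about 0-14% of the remaining variance. That is an interval up to about 7% narrower, or up to about 9% at the equal-correlation bound with r = 0.7, and roughly 0-3 points of power. Every correlation and reliability behind these ranges is assumed, because the documents give none. The direction is safer than the size: a prognostic covariate measured before randomisation costs about one degree of freedom per time point in a trial with 210 evaluable participants.

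**What to change.** 1. Check the REDCap data dictionary: does Section I store the PEG score from the pre-screen visit for everyone randomised?
2. Specify how baseline BPI-Total enters the primary model: either as a covariate for the post-baseline scores, or as an outcome row with baseline means constrained equal across arms. This does not depend on step 1. Handle each pain secondary outcome's own baseline score in the same way.
3. If the PEG is stored, add pre-screen PEG (continuous, centred) and PEG by time as fixed effects in the BPI-Total model and the pain secondary models, and report the STOMP contrast from that model.
4. If the PEG is stored, add it to the chained-equations imputation model, which matters with 25% dropout allowed for.
5. Date the change before any unblinded analysis. The covariate paragraph is written in the past tense, so the SAP should make clear whether analysis has begun. If it has, report the adjusted model as a named sensitivity analysis.

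The cost is one look at a data dictionary, a short SAP paragraph and a few model terms. No new data, visits or participants are needed, and the sample size does not change.

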All participants in the intervention group will also receive a REDCAP assessment at baseline, post-intervention (0-month, after all sessions are completed), and then at 3, 6, 9 and 12 months post-intervention. The primary outcome will be at 3 months, and a 1-month window will be allowed after each timepoint for the patient to be contacted and assessed. An important medical event form will be administered to each participant at post-intervention (0-month) to screen for any unexpected medical incident, the severity of the event, its relation to the study, and medical follow-up. Viral load will also be

collected at baseline and at 12 months. At baseline, if a viral load from the prior 6 months is available in the medical record, that value will be recorded; otherwise, a viral load will be drawn. At 12 months, if a viral load in the prior 3 months is available in the medical record, that value will be recorded; otherwise, a viral load will be drawn. We will continue to conduct assessments every six months until the end of the study for all participants who complete the intervention by the beginning of Year 3. Participants who completed the baseline assessment by April 30, 2021 will continue to receive outcome assessments until April 2023 for a maximum of 41 months or 3 years. These assessments may be conducted by phone, if necessary, or in person. They will also participate in an audio-recorded in-person qualitative interview at the mid-point and end of the trial which will be transcribed using a third party company.

We will also investigate the intervention's impact on use of prescribed and non-prescribed opioids. Study staff will ask at each baseline and outcome assessment (0,3,6,9,12) the name of the participants' pharmacies along with the list of their current medications and dosage. Study staff will print out the medication lists and review it against the Opioid Medication Resource to identify the prescribed opioids. With written consent and a signed release of information from participants, a study staff member will contact the participants' pharmacy (or pharmacies) at the 12-month assessment to verify the self-reported information provided by the participants in the prior assessments. The data will be added into an excel spreadsheet for collection and analysis. Participants will receive up to 3 reminder calls at about a week and 48 hours prior to the next outcome assessment.

Qualitative interviews

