prescreening, enrollment, randomization, timeline/window of outcome assessments, status of assessments, reminder call status for assessments and pharmacy data.. All study staff will be trained in Human Subjects Protections, and this data will be handled in accordance with CNICS electronic storage and data transfer guidelines.

Study staff will also review data entered in RedCap on a weekly basis as a quality assurance measure. The program manager at the University of Pittsburgh will provide oversight of data quality and will conduct monthly audits.

k) MANAGEMENT AND INTEGRATION OF UAB AND UNC SITES

Study PI [name] and Program Director [name] will conduct regular in-person visits to each site. Additionally, there will be a weekly video Skype meeting with [name], [name], and local study staff and site PIs at UAB and UNC. The purpose of these weekly meetings will be to track progress with study milestones, troubleshoot issues that may arise, and discuss any adverse events.

l) Assessment Table

STOMP								
Data Collection Instrument	Pre-Baseline (1)	Baseline (2)	0 Month Post (3)	3 Month Post (4)	6 Month Post (5)	9 Month Post (6)	12 Month Post (7)	LT Assessment(s) (8)
SECTION I	X							
SECTION II		X						
SECTION III			X	X	X	X	X	X

SECTION IV		X	X	X	X	X	X	X
SECTION V		X	X	X	X	X	X	X
SECTION VI		X	X	X	X	X	X	X
SECTION VII			X					

m) SNAP SHOT OF STUDY ACTIVITIES

Procedure	Length of Time Required of Participants	Frequency of Repetition
Individual sessions (intervention group only)	6 sessions, up to approx. 60 minutes each	Maximum of on average every other week
Group sessions (intervention group only)	6 sessions, up to approx. 60 minutes each	Maximum of on average every other week
REDCAP assessments – see attached	Approx 30 minutes	Baseline, (0-month), 3,6,9 and 12 months after intervention, and every 6 months until the end of the study for all participants who

		complete the intervention by the start of Y3
Mid-study calls (comparison group)	Approx 5 min	8 weeks after the beginning of the intervention
Viral load assessment	Approx 15 minutes	Baseline and 12 month assessment visit
Qualitative interviews (peers, intervention group only)	Approx up to 120 minutes	After 6 sessions are completed and after all 12 sessions are completed
Pre-screen reminder calls	Approx 5 minutes	48 hours before pre-screening in-person visit

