One-on-one and group reminder calls (peers, intervention group only)	Approx 5 minutes	Up to three reminder calls before the scheduled intervention date
Reminder calls at 0,3,6,9, 12 month-assessments, and every 6 months thereafter, if applicable	Approx 5 minutes	Up to three reminder calls,, 1 week prior to and 48 hours prior to scheduled assessment date.

n) SUMMARY OF COMPENSATION

Intervention group

In person for Prescreen	\$25
Screening/Enrollment (Baseline) visit	\$50
Mid-point qualitative interview	\$50
End of study qualitative interview	\$50
0, 3, 6, 9 and 12-month assessments	\$50 each
Longer term assessments (18, 24, 30, 36,41)	\$50 each
Control group	
In person for Prescreen	\$25
Screening/Enrollment (Baseline) visit	\$50
0, 3, 6, 9 and 12-month assessments	\$50
Longer term assessments(18, 24, 30, 36,41)	\$50 each

IV. DATA COLLECTION AND MANAGEMENT

All study documentation will be kept in locked file cabinets in in study personnel’s offices at UAB and UNC. RedCap database can only be accessed by STOMP personnel using UAB and UNC computers or encrypted laptops.

V. DATA ANALYSIS

A separate document will be submitted by the PI of the study for the statistical analysis plan.

VI. CRISIS PROTOCOL

As a general note, referrals can be made for crisis consultation at any time. The research staff will document the findings of his/her evaluation and the course of action taken.

Providers for the patient may be informed about the same. If it becomes apparent during data collection that a patient is in danger, is suffering, or is at risk for developing a clinically relevant physical or mental health condition (e.g., depression, suicide, self-injurious behaviors), relevant staff in the local clinic (e.g., professional mental health counselors, social workers, and nurses/providers) will be notified and standard procedures already in place in each clinic for ensuring the physical and mental well-being of patients will be followed (e.g., intervening and/or providing appropriate referral, as indicated).

VII. PROTECTION OF HUMAN SUBJECTS

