[name]	Data Analyst	University of Alabama at Birmingham
[name]	Qualitative Interviewer	University of Alabama at Birmingham
TBD	Research Staff	University of North Carolina at Chapel Hill
[name]	Data Manager UNC	University of North Carolina at Chapel Hill
[name]	Project Manager	University of Pittsburgh

Statistical Analysis Plan

Study Design & Objectives. Our overall objective is to evaluate a novel theory-based PSM intervention, “Skills TO Manage Pain” (STOMP) developed for people with HIV (PWH). The design of the proposed study is a multicenter parallel-group individually randomized group clinical trial. The primary outcome is to evaluate the efficacy of STOMP, a theory-based intervention tailored to improving chronic pain in PWH immediately post intervention. The secondary outcomes are to investigate additional pain outcomes and proximal outcomes as potential mediators of STOMP’s impact on chronic pain immediately post intervention and at 3 months.

The study will be conducted at 2 institutions in the United States (University of Alabama at Birmingham (UAB) and University of North Carolina at Chapel Hill (UNC)), and we will enroll adult patients, ages >18 years of age, consented to participate in the CFAR Network of Integrated Clinical Systems (CNICS), English-speaking, having at least moderate chronic pain, ability and willingness to attend the group sessions at the date/time specified, and no plans for major surgery during the study period that would interfere with study procedures.

The primary hypothesis is STOMP will decrease pain severity and improve function (as measured by BPI-total) in PWH. To test this hypothesis, we propose a two-arm randomized trial of STOMP vs. an enhanced usual care comparison condition. Our primary outcome will be Brief Pain Inventory (BPI)-Total score and will be measured at baseline and immediately post-intervention (~12 weeks after first intervention session). Our secondary outcomes will be changes in additional pain scales (PEG and BPI subscales of BPI-pain severity and BPI-interference), pain self-efficacy questionnaire (PSEQ), Patient Health Questionnaire (PHQ-8), and pain catastrophizing scale (PCS) between groups immediately post intervention. We will examine sustained differences in primary and secondary outcomes at 3 months post intervention.

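### The protocol places the primary outcome 3 months after the intervention, the SAP places it immediately after the intervention, and nothing reconciles the two.

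*Combined protocol and SAP*

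**What the plan says.** **Protocol.** Section III.d (Intervention, Assessments) schedules assessments at baseline, "post-intervention (0-month, after all sessions are completed), and then at 3, 6, 9 and 12 months post-intervention". The next sentence reads: "The primary outcome will be at 3 months, and a 1-month window will be allowed after each timepoint". Section III.m (snapshot of study activities) gives the same schedule: "Baseline, (0-month), 3,6,9 and 12 months after intervention". The assessment table in section III.l has separate columns for the 0-month and 3-month visits. Section III.e puts the comparison arm's 0-month visit 12 to 16 weeks after the first intervention session, with the 3-month visit following it. Section V (Data Analysis) says only: "A separate document will be submitted by the PI of the study for the statistical analysis plan".

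**SAP.** Study Design & Objectives states: "The primary outcome is to evaluate the efficacy of STOMP, a theory-based intervention tailored to improving chronic pain in PWH immediately post intervention". It names BPI-Total as the primary outcome, which "will be measured at baseline and immediately post-intervention (~12 weeks after first intervention session". On the later visit it says: "We will examine sustained differences in primary and secondary outcomes at 3 months post intervention". Under Statistical Analyses, the linear mixed models will "test differences between intervention and control conditions at the immediate post intervention and at 3 months". The primary hypothesis is then to be tested with the arms' least squares means at every time, and that sentence singles out no visit.

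**The concern.** The two documents give different visits for the primary outcome, and those visits answer different questions. One is whether STOMP has an effect when the programme ends. The other is whether an effect is present 3 months later. A behavioural intervention could do well on one and not on the other.

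If the two results disagree, each could be presented as primary by citing one of the trial's own documents. A reader holding the November 2019 protocol would see a result reported under the SAP as an unexplained departure from it.

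A lesser point adds to this. The SAP's sentence on the primary test does not write down the contrast or the alpha. Read with the SAP's objectives, the natural contrast is the between-arm difference at the immediate visit, but the reader has to infer it.

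**Working it through.** **1. Are these really two visits?**

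| Source | Immediate post-intervention visit | 3 months post-intervention |
|---|---|---|
| Protocol III.d, Assessments | 0-month assessment | Separate later assessment, named as primary |
| Protocol III.e, Assessments | 0-month, 12 to 16 weeks after first session | Follows the 0-month visit |
| Protocol III.l and III.m | Listed separately | Listed separately |
| SAP, Study Design & Objectives | Primary (about 12 weeks after first session) | Sustained differences |
| SAP, Statistical Analyses | Tested | Tested |

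One innocent reading is that the protocol's 3 months means about 12 weeks from the first session, which would be the SAP's visit. It fails because the preceding protocol sentence calls that visit 0-month and counts 3 months after it. The nominal gap is 3 months. With the 1-month window after each timepoint, the actual gap can run from 2 months (0-month visit late, 3-month visit on time) to 4 months (the reverse).

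**2. Does the sample size settle which visit is meant?** Inputs from the SAP's Sample Size Calculation: 210 evaluable, difference 1, SD 2.4, two-sample t-test, 25% dropout, 280 recruited. Allocation is 1:1 (protocol, Randomization), so 105 per arm. Alpha is not stated; two-sided 0.05 is assumed.

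- Standard error = 2.4 × √(2/105) = 0.331; noncentrality = 1/0.331 = 3.02.
- t-test power = 85.2%, against 85% stated.
- 210/(1 − 0.25) = 280, as stated.

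The plan's figures reproduce, but the calculation names no visit, so it does not decide between them.

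**3. How often would the visits disagree?** Treat the two test statistics as bivariate normal with correlation ρ (assumed 0.5 to 0.9) and two-sided 0.05. Then

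P(exactly one significant) = P(visit 1 significant) + P(visit 2 significant) − 2 × P(both significant).

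For a difference of 0.5 (an assumption), noncentrality = 0.5/0.331 = 1.51 and t-test power = 32.4%.

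| ρ | Difference 1 at both visits | Difference 1 at one, 0.5 at the other |
|---|---|---|
| 0.5 | 18.0% | 55.3% |
| 0.7 | 14.0% | 53.5% |
| 0.8 | 11.5% | 53.1% |
| 0.9 | 8.1% | 52.9% |

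A 40,000-trial simulation with t-tests gave 18.6%, 14.2%, 11.8% and 8.1% for the first column, and 55.2%, 53.1%, 52.5% and 52.5% for the second.

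**4. Hypothetical error rate.** Neither document says that either visit may be claimed as primary. If that were the rule, the false-positive rate under no effect would be 1 − P(neither significant) = 9.1%, 8.3%, 7.8% and 7.0% at the same four correlations. With independent tests it would be 1 − 0.95² = 9.75%.

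**The case against.** **The SAP governs the analysis.** The protocol hands data analysis to a separate SAP, and the SAP's objectives are consistent in placing the primary outcome at the immediate visit. The protocol's sentence sits in a scheduling paragraph and names no instrument. This gives a reasonable basis for following the SAP. It does not remove the conflict: the protocol says only that an SAP will be submitted, and no supplied text gives the SAP precedence or records a change of primary time.

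**The figures are largely assumed.** This stands. Alpha, the correlation and the 0.5 difference are not in the documents, and the 53% to 55% follows mainly from choosing 0.5. The calculations use simple t-tests, whereas the SAP plans a mixed model with a therapy-group random effect. The figures illustrate scale only; the contradiction rests on the text.

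**The choice of visit could affect power.** This stands as a qualification. If more participants were lost by the later visit, 280 recruited with the same difference and SD would give 82.7%, 79.8% or 76.6% power at 30%, 35% or 40% loss (assumed rates). The stated size holds only if the plan's difference, SD and 25% dropout apply at the visit chosen.

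**It may be too late to settle this blind.** Part of the SAP's Endpoint and Covariates section is in the past tense. That may be loose drafting and proves nothing, but the remedy should also work if results have already been seen.

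**Nothing suggests selective choice.** Agreed. A drafting slip in either document would look the same, the PIs and outcomes assessors are to be blinded, and no interim efficacy looks are planned.

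**Conclusion.** The contradiction holds and must be fixed. Protocol and SAP name different primary visits, nominally 3 months apart, and the supplied text neither reconciles them nor states precedence. Confidence is high because the conclusion rests on direct wording and on the protocol's own visit schedule.

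The practical effect depends on assumptions. If the planning effect held equally at both visits, the significance verdicts would differ in about 8% to 18% of trials; if the effect at one visit were half that at the other, in a little over half. The sample size of 210 evaluable and 280 recruited needs no change, subject to the condition on difference, SD and dropout given above. This is not a claim that the outcome was switched.

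**What to change.** 1. Before unblinded results are seen, state the same single primary time in the protocol (III.d, Assessments) and the SAP (Study Design & Objectives).
2. In the SAP's Statistical Analyses, define the primary contrast as the STOMP minus usual care difference in BPI-Total least squares means at that visit, with its two-sided alpha.
3. Label the other visit secondary in both documents.
4. If the SAP's time is kept, add a dated note giving the reason for the difference from the November 2019 protocol and saying whether outcome data by arm had been seen.
5. If that cannot be documented, including because results are already known, label the 3-month result as the protocol-specified primary when reporting. That analysis is already planned.

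**Cost:** one aligned sentence in each document (a protocol amendment and an SAP revision), one sentence for the contrast and alpha, and a short dated note. No participants, visits or analyses are added, because BPI-Total is already analysed at both visits.
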